Section to be changed		Clinical protocol synopsis, section 3.3.2. Inclusion criteria, section 3.3.3. Exclusion criteria
Description of change		Trial population in France is limited to adolescents 12 to 17 years old at Visit 2.
Rationale for change		Harmonisation of the CTP for the transition to EU Clinical Trials Regulation with inclusion of current Local Amendment 1 France requested by French Health Authority (ANSM) and already approved to limit the age groups to be enrolled in France.
Section to be changed		Flowchart footnote 13, Section 1.4.2. Table 1.4.2:1 overview of trial related risks, Section 5.2.3. Safety laboratory parameters, Section 6.2.2. treatment period(s), Section 10.9 Visit modification in exceptional circumstances– Table 10.9:1 Modification to visit procedures in exceptional

		circumstances
Description of change		Pregnancy testing will be done every 4 weeks for female patients in Poland and in Norway.
Rationale for change		Harmonisation of the CTP for the transition to EU Clinical Trials Regulation with inclusion of current Local Amendment 1 Poland (requested by Polish Authorities and already approved) and current local amendment 1 Norway (requested by the Norwegian Medicines Agency and already approved).
Section to be changed		Flow Chart:V3a and footnote 4
Description of change		For new patients in Norway, the Visit 3a is also applicable and should be performed at Week 6 (Day 43).
Rationale for change		Harmonisation of the CTP for the transition to EU Clinical Trials Regulation with inclusion of current Local Amendment 1 Norway requested and already approved by the Norwegian Medicines Agency.
Section to be changed		Flow Chart V12 - End of study
Description of change		V12 should be performed at Day 813 +/- 7 days V13 should be performed at Day 897 +/- 7 days V14 should be performed at Day 981 +/- 7 days V15 should be performed at Day 1093 +/- 7 days VX should be performed at Day 1093 +Q84 with time window of +/- 7 days
Rationale for change		Correction of calculation (1 day was missing)
Section to be changed		Flow chart – footnote 25 and Section 6.2.2 treatment period(s) – follow-up visit
Description of change		Sentences added: If the EoT visit has been delayed and has been done 28 days or more after the treatment discontinuation, the follow-up (FU) visit can be skipped.
Rationale for change		To limit the burden for the patient
Section to be changed		Flow chart – footnote 26 and Section 6.2.3 Follow-up and trial completion - End of Study visit
Description of change		Sentences added: In exceptional cases, when the patient is not able to come at site for medical reason, the EoS visit can be replaced by a phone call. If the EoT visit has been delayed and has been done 28 days or more after the treatment discontinuation, the EoS visit can be skipped.
Rationale for change		To limit the burden for the patient.
Section to be changed		Flow chart – footnote 28

Description of change		For patients who discontinue permanently trial treatment before Visit 15 and who accepted to attend further scheduled visits as per protocol, then the patient's trial completion will be at initial planned date of Visit 15 (at week 156) for roll-over patients and at the overall end of trial or, if earlier, when treatment options become or are made available for new patients.
Rationale for change		Correction following previous CTP revision
Section to be changed		Flow chart – footnote 28
Description of change		Sentence added: Completion of trial participation will be conducted at EoT visit, if FU/EoS visit is skipped due to delayed EoT for more than 28 days.
Rationale for change		To limit the burden for the patient
Section to be changed		Section 6.2.2 treatment period(s) –follow-up visit
Description of change		Sentence corrected: F-up visit should be conducted 28 days (+7 days) after the EoT visit for all discontinued patients who are not able to complete the remaining visits or who accepted the vital status collection.
Rationale for change		Correction
Section to be changed		Section 6.2.3 Follow-up period and trial completion – End of study visit
Description of change		Sentence updated: EoS visit should be conducted 28 days (+7 days) after the EoT visit for patients who have completed the trial on treatment as planned all patients except discontinued patients who are able to complete the remaining visits or who accepted the vital status collection. Sentence added: The EoS should be conducted at week 156 for prematurely discontinued roll-over patients who were able to complete the remaining visits off-treatment until week 156 and at the overall end of the trial for new patients who prematurely discontinued trial treatment and were able to stay in the trial until the overall end of trial.
Rationale for change		clarification
Section to be changed		Section 11.3 Global Amendment 3 description of change- change in section 3.1 (page 190)
Description of change		Roll-over patients will be considered as

		prematurely discontinued from trial treatment if they stop trial medication before week 156 (except at the age of 21) or if they stop trial medication after week 104 but without any other treatment option available.
Rationale for change		Correction in the description of the change

[figure not shown]
11.5 GLOBAL AMENDMENT 5

Date of amendment		27 Nov 2024
EU Clinical Trial No		2024-515743-27-00
BI Trial number		1199-0378
BI Investigational Medicinal Product(s)		Ofev [®] , nintedanib
Title of protocol		An open-label trial of the long-term safety and tolerability of nintedanib per os, on top of standard of care, over at least 3 years, in children and adolescents with clinically significant fibrosing Interstitial Lung Disease (InPedILD [®] -ON)
Global Amendment due to urgent safety reasons		
Global Amendment		x
Section to be changed		
		Title page
Description of change		
		The EU Clinical Trial Number was added
Rationale for change		
		Updated information.
Section to be changed		
		Synopsis –Duration of treatment
Description of change		
		The overall end of trial will take place approximately when last roll-over patient still on treatment is expected to reach reaches 3 years of treatment () ensuring that nintedanib or alternative treatment options (e.g., via marketing authorization, via compassionate use, or via similar process) will be available for all remaining patients (roll-over or new patients) outside the trial at this time.
Rationale for change		
		Clarification to avoid changing the timelines of overall end of trial in the last months of the study. In addition, as patients may travel long distances to expert centers, longer term planning needs to occur.
Section to be changed		
		Flow Chart - footnote 3, Section 4.2.1.2 Management of liver enzymes elevations, Table 4.2.1.2:1 Recommendations for managing liver enzyme elevations - footnote 4, Section 4.2.2.1. Restrictions regarding concomitant treatment,

		Section 5.2.3 Safety laboratory parameters – ‘a-Visits’ section, Section 6.2.2. Intermediate “a-Visits”
Description of change		Sentences adapted to clarify that the specific lab kit (visit-a) should be preferably used to monitor hepatic parameters, but local lab will be also acceptable.
Rationale for change		Clarification to limit the burden for the patient enable timely availability of safety lab and to give flexibility
Section to be changed		Flowchart – footnote 13, Section 1.4.2. Risks – table 1.4.2:1 Overview of trial related risks – Foetal harm, Section 5.2.3 Safety laboratory parameters – Pregnancy tests and Table 5.2.3:1 Safety laboratory tests at scheduled site visits, Section 6.2.2. other observations and procedures, Section 6.2.2. Intermediate pregnancy tests, Section 6.2.2. End of Treatment Visit, Section 6.2.2. Patients who prematurely discontinued trial treatment, section, Section 10.9 Visit modification in exceptional circumstances– Table 10.9:1 Modification to visit procedures in exceptional circumstances
Description of change		frequency of pregnancy testing harmonised: every 4-6 weeks (with every 4 weeks for female patients in Poland and Norway) Changed for all countries to: every 4 weeks .
Rationale for change		Harmonisation requested by Italian H.A. following transition to new regulation in Europe
Section to be changed		Flowchart – footnote 24 and section 6.2.2. Treatment period(s) - Patient who prematurely discontinued trial medication
Description of change		One sentence adapted to clarify that at remaining visits off-treatment visits, IRT call/notification is not needed anymore
Rationale for change		Clarification
Section to be changed		Flowchart –footnote 13 and footnote 24 and section 6.2.2. Treatment period(s) - Patient who prematurely discontinued trial medication
Description of change		In case of treatment discontinuation when a female patient continues with visits off treatment, then the urine pregnancy tests at home are only required to be continued every 4 weeks for the 3 months after last trial drug intake.

Rationale for change		To limit the burden of the patient.
Section to be changed		
Description of change		
Rationale for change		Change following authorities' interactions
Section to be changed		section 3.1 Overall trial design

2. LIST OF ABBREVIATIONS

Term	Definition / description
AE	Adverse event
AESI	Adverse event of Special Interest
ALK	Alkaline Phosphatase
ALT	Alanine Aminotransferase
AST	Aspartate Aminotransferase
BI	Boehringer Ingelheim
BMI	Body Mass Index
CKD-EPI	Chronic Kidney Disease - Epidemiology Collaboration
CTP	Clinical Trial Protocol
CTR	Clinical Trial Report
DBL	Database Lock
ECG	Electrocardiogram
eCRF	electronic Case Report Form
EDMS	Electronic Document Management System
eGFR	estimated Glomerular Filtration Rate
EMA	European Medicines Agency

Term	Definition / description
EoT	End of Treatment
GGT	Gamma-Glutamyl-Transferase
Hb	Haemoglobin
ICE	Intercurrent Event
ICH	International Conference on Harmonisation
ILD	Interstitial Lung Disease
INR	International Normalised Ratio
iPD	Important Protocol Deviation
IRT	Interactive Response Technology
ISF	Investigator Site File
KMED	Knowledge Management in Medicine
LLN	Lower Limit of Normal
MACE	Major Adverse Cardiovascular Events
MedDRA	Medical Dictionary for Regulatory Activities
N	Number
PD	Protocol Deviation

Term	Definition / description
[REDACTED]	[REDACTED]
PK	Pharmacokinetic(s)
[REDACTED]	[REDACTED]
PKS	Pharmacokinetics Set
[REDACTED]	[REDACTED]
PT	Preferred Term
pt-yrs	patient-years
[REDACTED]	[REDACTED]
REP	Residual Effect Period
SAE	Serious Adverse Event
SAS	Statistical Analyses Software as developed by SAS Institute
SCS	Screened Set
SD	Standard deviation
[REDACTED]	[REDACTED]
SSc	Systemic Sclerosis
[REDACTED]	[REDACTED]
SOC	System Organ Class
[REDACTED]	[REDACTED]
TMF	Trial Master File
TS	Treated Set
TSAP	Trial Statistical Analysis Plan
ULN	Upper Limit of Normal
[REDACTED]	[REDACTED]

3. INTRODUCTION

As per ICH E9 (1), the purpose of this document is to provide a more technical and detailed elaboration of the principal features of the analysis described in the protocol, and to include detailed procedures for executing the statistical analysis of the primary and secondary variables and other data.

This TSAP assumes familiarity with the Clinical Trial Protocol (CTP), including Protocol Amendments. In particular, the TSAP is based on the planned analysis specification as written in CTP Section 7 “Statistical Methods and Determination of Sample Size”. Therefore, TSAP readers may consult the CTP for more background information on the study, e.g. on study objectives, study design and population, treatments, definition of measurements and variables, planning of sample size, randomisation.

[figure not shown]
InPedILD[®]-ON is the open label extension of InPedILD[®] trial 1199.0337 which is also referred to as parent trial in this document.

Unless stated otherwise SAS[®] Version 9.4 will be used for all analyses.

[figure not shown]
4. CHANGES IN THE PLANNED ANALYSIS OF THE STUDY

In addition to the evaluations depicted in the CTP, the following evaluations will be added:

- Further endpoint analysis:

[figure not shown]

For patients who had a lung transplant during the trial, results after the lung transplant will not be considered for the analyses of

No safety data collected after a lung transplant will be excluded from the analyses.

As per CTP amendments 3 (29 Nov 2023) and 5 (27 Nov 2024) some additional timepoints have been added to some further safety and efficacy endpoints due to prolongation of the trial from 2 to 3 years:

5. ENDPOINTS

In this section, more details are given regarding endpoints. Please note that for all endpoints and analyses, [Section 6.7](#) should be consulted for baseline value definition.

Handling of missing data points is described in [Section 6.6](#).

For endpoints or other variables where derived “last contact date” is utilised, e.g. time-to-event analyses, the following will apply:

The derived last contact date when the patient was known to be alive is defined as the latest date recorded in the electronic Case Report Form (eCRF) from the dates listed below (in case an Adverse Event date is planned to be imputed for the analysis, the imputed date will also be used):

- Last visit date (including start or end date of a non-elective hospitalisation),
- Last reported Adverse Event (AE) date (excluding end dates when AE outcome is fatal or unknown),
- Last reported concomitant therapy date,
- Last laboratory sample date,
- Last reported trial drug intake date,
- Last reported dose change / interruption date,
- Last spirometry assessment,
- End of study participation date (as documented on End of Study eCRF page if reason for not completing the planned observation period is NOT “Death” or “Lost to Follow-up”).
- Last vital status date (as documented on Vital Status eCRF page if the patient is known to be alive),
- Last successful contact date (as documented on End of Study eCRF page if reason is “Lost to Follow-up”)

5.1 PRIMARY ENDPOINT

The primary endpoint is the incidence of treatment emergent adverse events over the whole trial. Thus, the number of patients experiencing at least one adverse event during the course of this extension trial will be analysed, see [Section 7.8](#).

[figure not shown]
5.2 SECONDARY ENDPOINT(S)

[figure not shown]
5.2.1 Key secondary endpoint(s)

[figure not shown]
This section is not applicable as no key secondary endpoint has been specified in the protocol.

[figure not shown]
5.2.2 Secondary endpoint(s)

[figure not shown]
This section is not applicable as no secondary endpoint has been specified in the protocol.

[figure not shown]

[figure not shown]

[figure not shown]

[figure not shown]

5.4 OTHER VARIABLE(S)

5.4.1 Demographics and baseline characteristics

5.4.1.1 Demographic data

[figure not shown]
- Gender (Male; Female)
- Race: single race respondents, multiple race respondents (all combinations ticked), and all race categories regardless of how many race categories were ticked
- Ethnicity (Hispanic/Latino; Not Hispanic/Latino)
- Age [years] at time of informed consent (transferred by IRT) as continuous variable and in categories [years] (6 to <12; 12 to <18; >=18)^[1]
- Weight [kg] at baseline as continuous variable and in categories [kg] (<13.5; 13.5 to <23.0; 23.0 to <33.5; 33.5 to <57.5; >=57.5)
- Height (standing) [cm] at baseline as continuous variable
- Body mass index [kg/m²] at baseline, calculated as

[figure not shown]
$$\frac{\text{Weight [kg]}}{\text{Height [m]} * \text{Height [m]}}$$

as a continuous variable

- Smoking status (Never, Current, Former)
- Household/second-hand smoking (No; Yes)

^[1] In France only patients >= 12 years were eligible for recruitment (local protocol amendment).

5.4.2 Compliance

Compliance [%] is assessed by the investigator per visit. For the analysis the reported values will be aggregated to an overall compliance per patient. If compliance is missing for at least one visit the overall compliance will be missing.

Overall compliance [%] will be summarised as continuous variable and in categories [%]:

- <50
- 50 to <80
- 80 to 120
- >120

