Duration of treatment	
Treatment duration for each patient will be variable.
 
For roll-over patients: at least 3 years; or until alternative treatment options become or are made available (e.g., via marketing authorization, via compassionate use, or via similar process) to the patient outside of the clinical trial.
 
For new patients: until the overall end of the trial (with expected minimum treatment duration of 76 weeks).
 
Exception: patients aged 21 years must complete the trial before their 22nd birthday. Consequently, a treatment duration of at least 3 years might not be reached by some patients aged 21.
 
The overall end of trial will take place approximately when last roll-over patient is expected to reach 3 years of treatment (██████████) ensuring that nintedanib or alternative treatment options (e.g., via marketing authorization, via compassionate use, or via similar process) will be available for all remaining patients (roll-over or new patients) outside the trial at this time.

Statistical methods	
Descriptive statistics will be provided for adverse events (██████████).

FLOW CHART V1-V11

Trial Periods	Screening	Treatment ³																		
Visits	1 ¹	2	3 ⁴	3a ^{3&4}	4	4a ³	5	5a ³	6	6a ³	7	7a ³	8	8a ³	9	9a ³	10	10a ³	11	11a ³
Weeks ²	-4		2		12		24		36		52		64		76		88		104	
Days ²	≤28d before D1	D1 ²	15		85		169		253		365		449		533		617		729	
Time window for visits (days)		none	±3		±3		±3		±7		±7		±7		±7		±7		±7	
Informed consent and assent ⁵	X																			
HRCT sent to central review ⁶	X																			
Biopsy sent to central review ⁷	X																			
Demographics	X																			
Medical history	X																			
Baseline conditions ⁸	X																			
██████████	X ³⁰																			
Physical examination, Vital signs ⁹	X	X	X		X		X		X		X		X		X		X		X	
Height (standing and sitting) ¹⁰	X	X			X		X		X		X		X		X		X		X	
Leg length		X			X		X		X		X				X				X	
Weight ¹⁰	X	X	X		X		X		X		X		X		X		X		X	
12 lead-ECG (at rest) ¹¹	X	(X)					X				X				X				X	
Safety Laboratory (blood and urine) ¹²	X ⁹	X	X	(X)	X	(X)	X	(X)	X	(X)	X	(X)	X	(X)	X	(X)	X	(X)	X	(X)
Pregnancy tests ¹³	X	X	X		X		X		X		X		X		X		X		X	
Dispense urine pregnancy test with Diary Card (if applicable) ¹³		X ¹³	X ¹³		X		X		X		X		X		X		X		X	
Review Diary Card for urine pregnancy test (if applicable) ¹³					X		X		X		X		X		X		X		X	
██████████		X			X		X		X		X									

Trial Periods	Screening	Treatment ³																		

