3.3 SELECTION OF TRIAL POPULATION

It is anticipated that at least 30 patients on treatment at the end of the InPedILD[®] trial, from approximately 40 sites in about 21 countries, will consent to participate (and thus receive treatment (if eligible)) in this trial.

In addition, considering enrolment of 2 patients/month across around 40 sites, approximately 20 to 30 newly identified patients are expected to enter treatment in an estimated recruitment period of 18 months with a screen failure rate around 50%. Extension of the study population beyond that of the parent trial is aimed at addressing a high unmet medical need for safe and efficacious therapy for fibrosing ILDs in children and adolescents.

Re-enrolment of screen failed patients will be permitted once. Patients who did not qualify for entering treatment during the early months of the recruitment period might qualify for entering treatment during the late months of the recruitment period of the study. A new informed consent/assent will be signed by the patient/parent(s)/legal guardian and the patient

will be assigned a new unique patient number. The previous patient number will be collected via the electronic Case Report Form (eCRF).

A log of all patients enrolled into the trial (i.e. who have an informed consent signed) will be maintained in the Investigator Site File (ISF) irrespective of whether they have been treated with investigational drug or not.

If retrospectively it is found that a patient has been entered in error (=did not meet all inclusion criteria or met one or more exclusion criteria), the sponsor or delegate should be contacted immediately. Based on an individual benefit-risk assessment by the investigator in discussion with the patient and its parents/legal guardian and discussion with the sponsor, a decision will be made whether continued trial participation is possible or not.

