- Dental examination: Previous panoramic x-ray within 12 weeks prior Visit 2 should be used as baseline. If a previous dental examination as outlined above is not available, a dental examination will be conducted according to protocol requirements (see [Section 5.2.6](#)) and evaluated at site.
- Dental imaging: Previous panoramic x-ray within 24 weeks prior Visit 2 should be used as baseline. If a dental imaging is not available as outlined above, a dental imaging will be conducted according to protocol requirements (see [Section 5.2.6](#)). The panoramic x-ray will be sent to central evaluation by a paediatric dentistry expert in a timely manner.

Visits 3, 4, 5, 6, 7, 8, 9, 10, 11, 12, 13, 14, 15, X (treatment period)

Additional clinic visits will be scheduled on regular basis from Visit 2 until End of Treatment (EOT) visit. Detailed procedures and assessment to be performed at each Visit are described in [Flow Chart](#) and [Section 5](#).

As the treatment duration for each patient will be variable, some visits may not apply (to some new patients and to some patients aged 21)

For roll-over patients with 26 weeks or more in InPedILD[®], Visit 3 is not needed. This additional visit is scheduled after 2 weeks of treatment to assure close monitoring of new patients and roll-over patients with less than 26 weeks in InPedILD[®], during the first month of study.

The following must be ensured during trial visits according to the study [Flow Chart](#):

[figure not shown]
- [REDACTED]

- FVC measurements at all visits should be performed approximately at the same time of the day to reference time point at Visit 2.

Observations and procedures:

Observations and procedures [redacted]:

Other observations and procedures:

- Compliance will be checked, and drug accountability will be completed.
- Criteria for dose reduction / interruption will be checked, if any.

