Intermediate lab tests (“a”-Visits) for safety monitoring may be conducted between scheduled visits, as needed at the discretion of the investigator or as recommended by the SMC.

- Blood and urine samples will be collected and submitted to the central laboratory for analysis.

Samples may be collected locally (e.g. by the general practitioner or a nurse). The Investigator or site personnel may give the patient/parent(s)/legal guardian written instructions and procedures to be followed, together with the trial lab kits for the respective ‘a-Visit’ to be used for collecting and shipping samples to the central laboratory (preferable option) or samples may be analysed locally.

Intermediate pregnancy tests

During the treatment period and the follow-up period a pregnancy test must be conducted in all female patients every 4 weeks.

Urine dipstick pregnancy test kits will be provided locally for use between visits when visit intervals are > 4 weeks. Test results must be documented in the patient’s pregnancy test diary card and transferred to the patient’s records at the next site visit.

Treatment period duration

Treatment duration for each patient will be variable.

Roll-over patients will be requested to stay in the trial for at least 156 weeks (until Visit 15). At week 156, roll-over patients who can be treated with nintedanib or alternative treatment options outside the clinical trial will have their EoT Visit. The remaining roll-over patients will continue in the trial until nintedanib or alternative treatment options become available to them outside the clinical trial.

Trial treatment will be stopped prematurely if a reason for withdrawal is met (refer to [Section 3.3.4](#)).

After week 156, if reason for study treatment discontinuation is that nintedanib or alternative treatment options become available for patient outside the clinical trial, then the patient will not be considered as early discontinued for treatment.

New patients will stay in the trial until the overall end of the trial (with expected minimum treatment duration of 76 weeks), then patients will perform the EoT Visit.

End of Treatment Visit

If a patient discontinues the study during a scheduled treatment visit, then the scheduled visit will be replaced by the EoT visit. As consequence, roll-over patients that discontinue trial treatment at week 156 should perform EoT visit instead of Visit 15.

Observations and procedures:

- [REDACTED]

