6.4 SUBJECT SETS ANALYSED

- Screened set (SCS):
This patient set includes all patients having signed informed consent.
- Treated set (TS):
This patient set includes all patients who were dispensed study medication and were documented to have taken at least one dose of investigational treatment.
- Pharmacokinetic set (PKS):
This patient set includes all patients from the Treated Set (TS) with at least one evaluable PK plasma concentration.

All evaluations for PK endpoints will be based on the PKS. All other analyses will be based on the TS, except for disposition which is based on the SCS.

[figure not shown]

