7. PLANNED ANALYSIS

Unless otherwise specified, all analyses described in this section will be done on the Treated Set. All available data (i.e. data for all available timepoints, as defined in [Section 6.7](#)) will be presented in the summary tables, irrespective if the timepoint is specified in the endpoint definition in the CTP. For endpoints with time intervals, only data for the intervals specified in the endpoint definition will be presented.

The labelling and display format of statistical parameters will follow BI standards (9). For End-Of-Text tables, the set of summary statistics is: N / Mean / SD / Min / Median / Max.

In descriptive statistics tables, mean, SD and median will be rounded to one additional digit than the raw individual value. For tables that are provided for endpoints with some extreme data, median, quartiles and percentiles should be preferred to mean, standard deviation, minimum and maximum.

Tabulations of frequencies for categorical data will include all possible categories and will display the number of observations in a category as well as the percentage (%) relative to the respective group (unless otherwise specified, all patients in the respective patient set whether they have non-missing values or not). The precision for percentages should be one decimal point. The category missing will be displayed only if there are actually missing values.

Unless otherwise specified, all analyses will be provided by patient group (initiated nintedanib or continued nintedanib) and overall (total):

[figure not shown]
- Group 1: Initiated nintedanib
 - New patients
 - Patients who prematurely discontinued treatment permanently in 1199-0337
 - Completed patients from 1199-0337 not able to roll over into the extension trial within 12 weeks following their End of Treatment visit in the parent trial (i.e. time period between last dose of trial drug in parent trial and first dose in extension trial is greater than 12 weeks)
 - Patients from 1199-0337 placebo arm Part A (i.e. from double-blind placebo arm who did not enter the open-label nintedanib period and only received placebo in the parent trial)
- Group 2: Continued nintedanib
 - Patients from 1199-0337 Part B (i.e. from open-label nintedanib period of the parent trial, time period between last dose of trial drug in parent trial and first dose in extension trial is less than or equal to 12 weeks)

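### One missing visit value voids a patient's overall compliance, so the continuous summary uses complete cases only and discards recorded data

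*SAP*

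**What the plan says.** Protocol 4.3 defines compliance as capsules taken over capsules that should have been taken, times 100. The flow chart places a check at Visits 3 to 15, at each later Visit X and at end of treatment (EoT). Protocol 6.2.2 also asks for one at unscheduled visits for a dose reduction, dose increase or change of capsule size.

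SAP 5.4.2 aggregates the visit values to one overall percentage per patient, without giving the aggregation formula, and then states: "If compliance is missing for at least one visit the overall compliance will be missing". The result is shown as a continuous variable and in four categories. SAP 6.6 does not impute missing data in general, and no visible exception covers compliance.

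For continuous variables SAP 7 says "the set of summary statistics is: N / Mean / SD / Min / Median / Max". For categorical tables it keeps all patients of the set in the denominator unless stated otherwise, and "The category missing will be displayed only if there are actually missing values". On analysis sets, SAP 6.4 says: "All other analyses will be based on the TS, except for disposition which is based on the SCS". Compliance plays no part in defining them.

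**The concern.** The rule treats a patient with eleven of twelve values the same as a patient with none. In the continuous summary both disappear, so the mean and median describe only patients with an unbroken record. In the category table the voided patient moves to the missing row but stays in the denominator, which lowers the reported percentage in the 80 to 120 band.

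Gaps are foreseeable. Under Protocol 6.1 a visit postponed into the next visit's window is skipped. Under Table 10.9:1 drug may be shipped to the patient and the remainder returned later. An interval in which no drug was due leaves the Protocol 4.3 ratio without a denominator, and SAP 5.4.2 does not say how such an interval counts.

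What is at stake is the usefulness of one descriptive summary. It is the only visible measure explicitly built on capsule counts: total dose in SAP 5.4.3 is days on each dose times twice that dose, so missed capsules do not enter it.

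**Working it through.** The plan gives no figure for missing compliance, so there is nothing to reproduce.

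**Number of scheduled checks, k**

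- Roll-over patient with 26 weeks or more in the parent trial: "Visit 3 is not needed" (Protocol 6.2.2). Checks fall at Visits 4 to 14 and then EoT, because "roll-over patients that discontinue trial treatment at week 156 should perform EoT visit instead of Visit 15". That is 11 + 1 = 12. The intervals are nine of 12 weeks and three of 16 weeks: 108 + 48 = 156 weeks. A roll-over patient who does have Visit 3 has 13.
- New patient at the 76-week expected minimum (Protocol synopsis): Visits 3 to 9, the last as EoT, so k = 7. The intervals are 2 + 10 + 12 + 12 + 16 + 12 + 12 = 76 weeks.
- Other new patients: Protocol 3.3 expects them to "enter treatment in an estimated recruitment period of 18 months", which is 78 weeks. Assuming even recruitment and 76 weeks for the last patient entered, a mid-recruited patient reaches 76 + 39 = 115 weeks (Visits 3 to 11 plus EoT, k = 10). The earliest reaches 76 + 78 = 154 weeks (Visits 3 to 14 plus EoT, k = 13).

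Unscheduled checks would raise k by an amount that cannot be derived from the documents.

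**Chance that the overall value is missing**

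Assume a fraction p of values is missing per check.

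- Independent gaps: 1 − (1 − p)^k. For k = 12 and p = 2%: 1 − 0.98^12 = 21.5%.
- Clustered gaps: beta-binomial with mean p and within-patient correlation 0.2. With a = 4p and b = 4(1 − p), the chance is 1 minus the product of (b + i)/(a + b + i) over i = 0 to k − 1.

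| k | Independent, p = 1% / 2% / 5% | Correlation 0.2, p = 1% / 2% / 5% |
|---|---|---|
| 7 | 6.8 / 13.2 / 30.2% | 4.3 / 8.4 / 20.0% |
| 10 | 9.6 / 18.3 / 40.1% | 5.3 / 10.3 / 23.9% |
| 12 | 11.4 / 21.5 / 46.0% | 5.8 / 11.3 / 26.0% |
| 13 | 12.2 / 23.1 / 48.7% | 6.0 / 11.7 / 27.0% |

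If the 30 roll-over patients that the protocol expects as a minimum all had 12 checks, independent gaps would void 30 × 11.4% = 3.4, 30 × 21.5% = 6.5 or 30 × 46.0% = 13.8 of them. With correlation 0.2 the numbers are 1.7, 3.4 or 7.8.

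**What is discarded**

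Among affected 12-check patients the mean number of recorded values is 12 − 12p/[1 − (1 − p)^12]. This gives 10.9, 10.9 and 10.7 for the three rates if gaps are independent, and 9.9, 9.9 and 9.7 if clustered. One missing 12- or 16-week interval still leaves 1 − 12/156 = 92.3% or 1 − 16/156 = 89.7% of the treatment time documented. With 7 checks, one gap leaves between 1 − 16/76 = 78.9% and 1 − 2/76 = 97.4%.

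**Does the loss differ between groups?**

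At equal p it rises with k, but 12 against 7 is the extreme contrast. For 12 against 10 the gap is at most 46.0 − 40.1 = 5.9 percentage points. The earliest new patients, with 13 checks, lose slightly more than roll-over patients with 12. Unequal p can also cancel the gap: 7-check patients lose as much as 12-check patients when their rate is 1 − (1 − p)^(12/7) = 1.7%, 3.4% or 8.4%, about 1.7 times p.

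**The case against.** The rule is stated openly and fits the SAP's reluctance to impute. SAP 6.6.3.3.2 does the same for interruptions, where one incomplete date makes the patient's total interruption duration missing. The parallel is imperfect: a sum with a missing component is too low, whereas a ratio over the documented intervals can still be interpreted if its coverage is shown.

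The loss will be visible, through N and the missing category. Duration of exposure, interruptions, total dose and dose intensity are reported separately, and the trial is descriptive throughout. All of this stands and keeps the point minor.

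The missingness rates are assumptions, and several provisions work against gaps: patients return all medication and packaging, the monitor verifies compliance (Protocol 4.3), and home visits collect medication (Table 10.9:1). This stands too. The documents cannot show whether the loss will be material. Parts of SAP 6.6 and 7 are also not visible, although an exception there would have to override an explicit sentence in 5.4.2.

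A reader might infer that the rule biases the comparison of the two patient groups, because roll-over patients are checked more often. The documents do not support that. Check counts overlap and can reverse, unscheduled checks vary by patient, and the initiated-nintedanib group in SAP 7 also contains roll-over patients from the parent trial's Part A placebo arm.

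Averaging the available intervals has its own risk: it overstates compliance if the missing intervals were the poorly adherent ones.

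**Conclusion.** The point holds as an optional improvement. Read literally, SAP 5.4.2 removes from the compliance mean and median a patient with about 90% of three years documented. The share affected depends on a missingness rate that the documents do not give: 6% to 46% of 12-check patients over the assumed range of 1% to 5% per check, from clustered to independent gaps.

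Two stronger conclusions might be drawn, and neither is supported. The direction of any bias in the compliance mean, or between groups, is not established. Nor is any safety result affected: the treatment-emergent adverse event analysis runs on the Treated Set, which requires only one documented dose, and compliance enters no other visible derivation.

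**What to change.** Replace the sentence in SAP 5.4.2 along these lines:

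1. Derive overall compliance from all on-treatment intervals with a reported value, weighting each visit percentage by the days on which drug was due, with recorded interruptions excluded. Off-treatment periods are already defined in SAP Table 6.1:1. If capsule counts are in the database, use total capsules taken over total capsules due instead, which follows Protocol 4.3 directly. Weighting by calendar length alone would give too much weight to intervals containing long interruptions.
2. Treat an interval with no drug due as not applicable, not as missing. State also how skipped visits and unscheduled checks are handled.
3. Report the share of drug-due time covered, by patient group and overall.
4. Set the value to missing only below a coverage threshold fixed in the SAP before database lock, for example 75%. A single 16-week gap then voids a patient only if fewer than 16/0.25 = 64 weeks of drug were due. A patient with 76 weeks of treatment and up to 12 weeks of interruption outside the gap is kept.
5. Keep the complete-case summary as a sensitivity display. The SAP history table shows that an interim report has been prepared, and SAP 10.1 applies the final methodology to interim analyses, so this also preserves comparability.

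The cost is a few SAP sentences and minor programming. No new data are needed if the visit percentages are used; the capsule version needs confirmation that counts were captured. Overstatement remains possible if the missing intervals were poorly adherent, but the coverage figure shows how much is missing.
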